## 1.0 SUMMARY

**Background:** Our research group has shown that high interleukin (IL)-13 is associated with respiratory failure in COVID-19 and that IL-13 inhibition protects in a mouse model of SARS-CoV-2 infection. IL-13 is a known cause of pulmonary inflammation in asthma and interstitial lung disease. We have discovered that IL-13 neutralization lessens the severity of COVID-19 and reduces hyaluronan (HA), an extracellular matrix polysaccharide previously implicated in other inflammatory pulmonary diseases, deposition in mouse lung parenchyma. It is therefore biologically plausible that IL-13 contributes to the long-haul pulmonary compromise seen in patients with severe COVID-19, potentially through promotion of HA synthesis. We hypothesize that neutralization of IL-13 will protect from acute and chronic pulmonary damage by blocking acute HA synthesis and inflammation downstream of IL-13.

**Clinical Experience:** We have conducted a phase IIa randomized double-blind placebo-controlled trial to assess the safety and efficacy of dupilumab plus standard of care versus placebo plus standard of care in mitigating respiratory failure and death in those hospitalized with COVID-19 (HSR 210184, enrollment completed/closed November 2021). Through this trial we found that dupilumab was safe for use in this population and that there was a reduced 60-day mortality in those who received dupilumab plus standard of care regimens versus placebo plus standard of care regimens. These findings implicate dupilumab as a promising and novel treatment for those hospitalized with COVID-19. Given this, along with our pre clinical data showing IL-13 influence on pulmonary injury, we plan to determine differences in post recovery pulmonary function between those who were randomized to the dupilumab arm versus placebo during acute COVID-19 infection in the HSR 210184 study cohort 1 year after enrollment.

**Primary Objective:**

- Determine the difference in post recovery pulmonary function between those randomized to dupilumab arm versus placebo for acute moderate to severe COVID-19.

**Primary Endpoint:**

- Proportion of patients with abnormal diffusing capacity for carbon monoxide (DLCO) and/or 6 minute walk testing 1 year after acute COVID-19 infection.

**Secondary Objectives:**

- Evaluate the immunologic and biologic end points of inhibition of type 2 inflammation post recovery from COVID-19 in the dupilumab arm compared to placebo.
- Evaluate imaging abnormalities post recovery from COVID-19 in the dupilumab arm compared to placebo.
- Evaluate long haul symptom incidence post COVID-19 recovery in the dupilumab arm compared to

placebo.

#### **Secondary Endpoints:**

- Proportion of patients with new systemic, respiratory, musculoskeletal, neuropsychiatric and/or cardiac symptoms post COVID-19 consistent with long haul syndrome (fatigue, poor concentration, daily activity restriction, chronic malaise, asthenia, dyspnea, persistent cough, pleurisy, sleep abnormalities, chronic headache, olfactory impairments, gustatory impairments, brain fog, memory defects, depression, anxiety, dizziness, myalgias, joint pain, chest pain, palpitations): 1 year after HSR 210184 enrollment
- Proportion of patients with reduced neurocognitive function: 1 year after HSR 210184 enrollment
- Proportion of abnormal predicted forced expiratory volume (FEV1), forced vital capacity (FVC) and/or total lung capacity (TLC): 1 year after HSR 210184 enrollment
- Proportion of patients with new oxygen requirement after COVID-19 hospitalization: 1 year after initial enrollment
- Proportion of patients with greater than 3% oxygen desaturation during 6 minute walk testing: 1 year after HSR 210184 enrollment
- Plasma cytokine levels including TARC (CCL17), YKL40, eotaxin 3 (CCL26), IL-13, IL-4, Arg1, Hyaluronan, soluble ST2: 1 year after HSR 210184 enrollment
- Differences in high resolution computed tomography (HRCT) chest scan appearance post recovery: 1 year after HSR 210184 enrollment

**Study Design:** As an extension to the randomized double-blind placebo-controlled trial assessing dupilumab for treatment of those hospitalized with acute moderate to severe COVID-19, this is a follow up assessment of this study cohort post recovery from COVID-19 for evaluation of pulmonary function testing (PFT), pulmonary imaging, immune biomarkers and symptoms. All data will be collected at a single follow up visit 1 year after initial enrollment in the parent study HSR 210184 .

#### **Study Population:**

##### **Inclusion Criteria:**

- Subjects that were enrolled in study protocol HSR 210184 per inclusion criteria below:
  - Male or female 18 years of age or older at the time of enrollment.
  - Patients hospitalized with a positive RT-PCR for SARS-CoV-2 within the last 14 days, with illness duration within the last 14 days, and evidence of moderate to severe COVID-19 infection as defined by NIH COVID-19 Severity Categorization (8):
    - Moderate illness: Individuals who show evidence of lower respiratory disease during clinical assessment or imaging and who have saturation of oxygen  $\text{SpO}_2 \geq 94\%$  on room air at sea level.
    - Severe illness: Individuals who have  $\text{SpO}_2 < 94\%$  on room air at sea level, a ratio of arterial partial pressure of oxygen to fraction of inspired oxygen ( $\text{PaO}_2/\text{FiO}_2$ )  $< 300 \text{ mm Hg}$ , respiratory frequency  $> 30 \text{ breaths/min}$ , or lung infiltrates  $> 50\%$ .
  - Patient and/or legally authorized representative is willing and able to provide written informed consent and comply with all protocol requirements.
  - Patients with hematologic malignancies or solid tumors are eligible.
  - Patients with autoimmune disorders are eligible.
  - Patients with immunodeficiency and organ or stem cell transplant recipients are eligible.
  - Patients with acute or chronic renal injury/failure are eligible.
  - Patients with neutropenia/lymphopenia are eligible.

---

Plasma cytokines will be measured using the MILLIPLEX® MAP Human Cytokine/Chemokine/Growth 28 Factor Panels, and individual Simplex or ELISA kits.

- Patients with elevated liver function tests are eligible.
- Women who are not taking contraception are eligible.
- Patients who are currently or have recently received steroids and/or remdesivir are eligible.
- Patient agrees to not participate in another clinical trial for the treatment of COVID-19 through end of study period.

**Exclusion Criteria:**

- Subjects enrolled in study protocol HSR 210184 no longer alive, able or willing to complete follow up visit at 1 year after enrollment.
- Any woman who is currently pregnant, or who could be pregnant due to menses history/positive pregnancy test

**Assessment and Data Acquisition (1 year after HSR 210184 enrollment):**

1. Pulmonary function testing: diffusing capacity for carbon monoxide (DLCO), 6 minute walk testing (6MWT), predicted forced expiratory volume (FEV1), predicted forced vital capacity (FVC) and predicted total lung capacity (TLC)
2. High resolution computed tomography (HRCT) imaging of chest
3. Symptom assessment via questionnaire: fatigue, poor concentration, daily activity restriction, chronic malaise, asthenia, dyspnea, persistent cough, pleurisy, sleep abnormalities, chronic headache, olfactory impairments, gustatory impairments, brain fog, memory defects, depression, anxiety, dizziness, myalgias, joint pain, chest pain, palpitations
4. Neurocognitive testing via questionnaire
5. Plasma cytokine levels including TARC (CCL17), YKL40, eotaxin 3 (CCL26), IL-13, IL-4, Arg1, Hyaluronan, soluble ST2

**Immune Evaluations:** Immune evaluations will be performed to assess the extent to which dupilumab administration influences immune markers post recovery from their COVID-19 hospitalization. IL-4, IL-13, TARC (CCL17), YKL40, eotaxin 3 (CCL26), Arg1, Hyaluronan, soluble ST2 and levels of other Th1/Th2 serum cytokines will be measured 1 year after HSR 210184 enrollment.

---

Plasma cytokines will be measured using the MILLIPLEX® MAP Human Cytokine/Chemokine/Growth Factor Panels, and individual Simplex or ELISA kits.

## **List of Abbreviations**

ADR	Adverse Drug Reaction
ADE	Antibody-mediated enhancement of infection
BP	Blood pressure
CT	Computed Tomography
DAIDS	Common Terminology Criteria for Adverse Events
DBP	Diastolic Blood Pressure
DLT	Dose limiting Toxicity
DSMB	Data and Safety Monitoring Board
ECG/EKG	Electrocardiogram
EUA	Emergency Use Authorization
FDA	Food and Drug Administration
GCP	Good Clinical Practice
IB	Investigator's Brochure
ICF	Informed Consent (Informed Consent Form)
ICH	International Conference on Harmonization
ICU	Intensive Care Unit
IEs	Immune Evaluations
IEC	Independent ethics committee
IL	Interleukin
IND	Investigational New Drug Application
IRB	Institutional review board
LOS	Length of Stay
LVEF	Left Ventricular Ejection Fraction
MERS	Middle East Respiratory Syndrome
NA	Nuclear antibody
NP	Nasopharyngeal
OP	Oropharyngeal
OS	Overall Survival
PBMC	Peripheral Blood Mononuclear Cells
PI	Principal Investigator
Pts	Patients
RT-PCR	Reverse Transcriptase Real-Time Polymerase chain reaction
PFT	Pulmonary Function Testing
PK	Pharmacokinetic
SAE	Serious adverse event
SARS	Severe Acute Respiratory Syndrome
SARS-CoV-2	Severe Acute Respiratory Syndrome Coronavirus 2
SBP	Systolic Blood Pressure
SOC	Standard of Care
UP	Unanticipated Problem
UPnonAE	Unanticipated Problem that is not an Adverse Event

## 2.0 OBJECTIVES

### 2.1 Primary Objective

- Determine the difference in post recovery pulmonary function between those randomized to dupilumab arm versus placebo for acute moderate to severe COVID-19.

### 2.2 Secondary Objectives

- Evaluate the immunologic and biologic end points of inhibition of type 2 inflammation post recovery from COVID-19 in the dupilumab arm compared to placebo.
- Evaluate imaging abnormalities post recovery from COVID-19 in the dupilumab arm compared to placebo.
- Evaluate long haul symptom incidence post COVID-19 recovery in the dupilumab arm compared to placebo.

### 2.3 Study Design

As an extension to the randomized double-blind placebo-controlled trial assessing dupilumab for treatment of those hospitalized with acute moderate to severe COVID-19, this is a follow up assessment of this study cohort post recovery from COVID-19 for evaluation of pulmonary function testing (PFT), pulmonary imaging, immune biomarkers and symptoms. All data will be collected at a single follow up visit 1 year after initial enrollment.

## 3.0 BACKGROUND AND SIGNIFICANCE

### 3.1 Background and Scientific Rationale

We have discovered that COVID-19 patients with high plasma interleukin (IL)-13 levels have a significantly greater risk of needing mechanical ventilation. IL-13, which signals through the receptor IL-4R $\alpha$  along with the closely related cytokine IL-4, is involved in eosinophilic inflammation, mucous secretion, goblet cell metaplasia and fibrosis, and has been regularly implicated in airway hyperresponsiveness and atopic disease. We additionally found that neutralization of IL-13 in K18-hACE2 C57Bl/6J mice protected the animals from severe infection with SARS-CoV-2, as evidenced by reduced clinical score, weight loss and mortality. The association of IL-13 along with other effectors of type 2 immunity with respiratory failure from COVID-19 has also been demonstrated in other observation studies. These findings established mechanistic and biologic plausibility for IL-13 as a driver of pulmonary injury in COVID-19.

RNA-seq analysis of whole lung tissue taken from infected mice who underwent IL-13 neutralization revealed the most downregulated gene to be Has1, which encodes a synthase responsible for hyaluronan (HA) production, a polysaccharide apart of the extracellular matrix that has previously been implicated in other inflammatory pulmonary diseases. This was mechanistically further supported by an increase in HA deposition in human and mouse lung with SARS-CoV-2 infection. Additionally, neutralization of the HA receptor, CD44, led to improved survival. As HA has been proposed previously in asthma as a potential culprit in airway remodeling, this led to the hypothesis that HA, as a downstream effector of IL-13, may be involved in pulmonary dysfunction post recovery from COVID-19.

We tested our hypothesis that IL-13 leads to post-recovery pulmonary dysfunction in COVID-19 in a pilot cohort of 55 patients from the UVA Post-COVID-19 clinic who were hospitalized for severe to critical COVID-19 (79% requiring mechanical ventilation). Pulmonary function tests (PFTs) were measured from 1-8 months post recovery, focusing on DLCO (diffusing capacity for carbon monoxide) and 6MWT (six-minute walk test) as prior data in ARDS and COVID-19 implicated these in post recovery pulmonary abnormalities. We discovered that patients with high IL-13 during admission were almost 2.4 times as likely to have an abnormal 6MWT or abnormal DLCO post recovery from COVID-19 when adjusting for race/ethnicity, body mass index, smoking status and days from symptom onset (DFSO) to acute sample collection. Although it is fully recognized that this represents a preliminary exploratory analysis, especially given the small sample size and biomarker heterogeneity in acute disease, this initial

evidence of acute type 2 immune impact on post recovery pulmonary function is an exciting finding and, at the very least, warranting of further investigation.

### **3.2 Experience with the use of dupilumab in COVID-19**

Dupilumab, an anti-interleukin-4 receptor- $\alpha$  monoclonal antibody, leading to blockage of IL-4 and IL-13 signaling, has been FDA approved for treatment of moderate to severe atopic dermatitis since 2017. It has been successfully shown to reduce disease severity in not only those with atopic dermatitis but in other allergic diseases where Th2 cytokines have been implicated, including asthma and chronic rhinosinusitis. Original clinical trials noted excellent safety profiles in addition to favorability in its use when considering the negative impacts of long term steroid use in these patients.

We have previously conducted a phase IIa randomized double-blind placebo-controlled trial to assess the safety and efficacy of dupilumab plus standard of care versus placebo plus standard of care in mitigating respiratory failure and death in those hospitalized with COVID-19. Subjects were followed prospectively for 60 days, with collection of clinical outcomes, adverse events and immunologic biomarkers at multiple time points throughout the study period. Through this trial we found that dupilumab was safe to use for this indication, that there was reduced 60-day mortality in those who received dupilumab compared to placebo and that there was a trend toward reduction in ICU admission in the dupilumab group, all of which implicated dupilumab as a promising treatment for those hospitalized with moderate to severe COVID-19.

## **4.0 ELIGIBILITY**

### **4.1 Inclusion Criteria**

- Subjects that were enrolled in study protocol HSR 210184.

### **4.2 Exclusion Criteria**

- Subjects enrolled in study protocol HSR 210184 no longer alive, able or willing to complete follow up visit at 1 year after enrollment.
- Any woman who is currently pregnant, or who could be pregnant due to menses history/pregnancy test

## **5.0 STUDY TIMELINE**

### Telephone call to discuss follow up visit on Day 365 $\pm$ 90 days after enrollment for HSR 210184:

1. Discuss and consent for follow up visit and procedures
2. Schedule follow up visit

### Follow Up Visit on Day 365 $\pm$ 90 days after enrollment for HSR 210184 to discuss participation in 220171:

1. Urine pregnancy test at the time of consenting to rule out participation
2. Blood for immune evaluation of cytokine levels (1 light green top, 3 mL/draw)
3. CT chest imaging (non-contrast)
4. Pulmonary function testing (spirometry, lung volumes, diffusing capacity for carbon monoxide (DLCO), 6 minute walk testing (6MWT))
5. Symptom screen (fatigue, poor concentration, daily activity restriction, chronic malaise, asthenia, dyspnea, persistent cough, pleurisy, sleep abnormalities, chronic headache, olfactory impairments, gustatory impairments, brain fog, memory defects, depression, anxiety, dizziness, myalgias, joint pain, chest pain, palpitations)
6. Neurocognitive testing via questionnaire

### **5.1 Known potential benefits**

Subject recovery from COVID-19 will be assessed by a Pulmonary and Critical Care attending at follow up visit. Subjects will be provided with recommendations based on any abnormalities found.

## 5.2 Known potential risks

1. PFT: Dizziness, coughing, shortness of breath and/or provocation of asthma attack with deep inhalation during testing.
2. HRCT scan: radiation exposure, harm to unborn children.
3. Phlebotomy: local discomfort, bruising and/or hematoma, bleeding, fainting, infection. Total blood draw not to exceed 5mL.

## 6.0 STATISTICAL CONSIDERATIONS

### 6.1 Statistical analysis

All subjects who received one dose of study drug will be included in the safety analysis. Each primary and secondary efficacy outcome measure will be analyzed for the intent-to-treat (ITT) and evaluable population. The intent-to-treat principle is that participants will be analyzed in the groups to which they were randomized, regardless of whether they received the randomized study medication.

Data will be summarized as frequency with percentage for categorical clinical variables, and as mean  $\pm$  standard deviation or median with interquartile range for continuous variables. The difference between dupilumab and placebo arms will be tested with Chi-square for categorical measures (e.g., the primary endpoint) and two-sample t-test or Wilcoxon rank sum test for continuous measures (e.g., biomarkers). Due to the relatively small sample size in the study, the adjusted treatment effect of dupilumab will be estimated exploratively in generalized linear regression for the primary and secondary outcomes to account for the potential impact of patient characteristics (e.g., age, sex, race and co-morbidities) and baseline biomarker measures. Data transformation will be considered for the outcomes with skewed distribution. The difference in the biomarker measures at the follow-up visit and their changes from baseline between dupilumab and placebo groups will also be assessed. Since this is intended to be an early stage, proof of concept study for which the primary goal is to inform future trials rather than to perform formal hypothesis testing, no multiplicity adjustment is planned.

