### 6.2 Sample Size justification

Under the protocol HSR 210184, we conducted a randomized double-blind placebo-controlled trial assessing the safety and efficacy of dupilumab for treating hospitalized patients with acute moderate to severe COVID-19, which was designed as an early stage (Phase IIa) and proof of concept study. A total of 40 patients were enrolled from June 23, 2021 through November 180 11, 2021 in the Phase IIa study, and 7 of them died by Day 60. The sample size of 40 in the original Phase II study were determined largely based on the feasibility with a primary goal to collection reliable data and obtain sufficient evidence for future trials. The current proposed study is an extension of the original Phase IIa study under the HSR 210184, to assess the post recovery of remaining 33 patients from COVID-19 with respect to pulmonary function testing (PFT), pulmonary imaging, immune biomarkers and symptoms at one-year follow-up. All data will be collected at a single visit, 1 year (i.e.,  $365 \pm 90$  days) after initial enrollment in the remaining 33 parents from the study HSR 210184. Formal sample size estimation and power analysis is not performed due to the pilot nature of this proposed follow-up study.

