## 13.0 STOPPING DECISION RULES

The study enrollment will be stopped and reviewed by the PI if any of the following specific events occur or, if in the judgement of the study physician, subject safety is at risk of being compromised during the visit:

- Death due to study procedure
- Occurrence of a life threatening allergic/hypersensitivity reaction (anaphylaxis), manifested by bronchospasm with or without urticaria or angioedema requiring hemodynamic support with pressor medications or mechanical ventilation due to any of the study procedures performed (pulmonary function testing, blood collection)
- One subject with a grade 4 or persistent grade 3 ( $\geq 72$  hours) associated with study procedures

- Two subjects with persistent Grade 3 ( $\geq$  72 hours) or higher lab toxicity for the same parameter associated with study procedures
- An overall pattern of symptomatic, clinical, or laboratory events that the study investigators consider associated with study product and that may appear minor in terms of individual events but that collectively may represent a serious potential concern for safety.
- Any other event(s) which is considered to be a serious adverse event in the good clinical judgment of the attending physician team. This will be appropriately documented.

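### The extension's safety set is defined by receipt of parent-trial drug, although the extension gives no drug and its own risks come from the visit procedures

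*Protocol*

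**What the plan says.** Protocol 6.1 gives one rule for the safety population: "All subjects who received one dose of study drug will be included in the safety analysis". It sets no condition on consent to the extension, on attendance or on having a procedure.

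The rest of the protocol describes a study without drug administration.

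- **What is done.** Section 5.0 lists a telephone call and a single visit: pregnancy test, blood sample, chest CT, lung function and walk tests, symptom screen and neurocognitive questionnaire.
- **What can go wrong.** Sections 5.2 and 9.2 list risks of lung function testing, CT and phlebotomy only. Four of the six stopping criteria in 13.0 are tied to procedures, for example a severe hypersensitivity reaction "due to any of the study procedures performed (pulmonary function testing, blood collection"). One of the other two refers to study product.
- **Who can enter.** Section 4.1 requires parent enrolment only: "Subjects that were enrolled in study protocol HSR 210184". Section 4.2 excludes "Subjects enrolled in study protocol HSR 210184 no longer alive, able or willing to complete follow up visit". Section 8.4 counts a person as enrolled once re-consent is signed.
- **How many.** Section 6.2 reports 40 parent enrolees, "and 7 of them died by Day 60", and the aim "to assess the post recovery of remaining 33 patients from COVID-19".
- **When adverse events are documented.** Section 10.6 starts the period at the first dose of study product and ends it 60 days later, or at un-enrolment if that comes sooner.

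The SAP describes the parent drug trial. Its section 3.1 uses the same at-least-one-dose rule for safety.

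**The concern.** A safety set should contain the people exposed to whatever may cause harm. In the parent trial that was an injection, so a dosing rule was right. In the extension it is a set of visit procedures, and having had a dose about a year earlier neither implies nor is required for exposure to them.

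The mismatch can run in two directions. Dosed parent patients who never came to the visit may be counted as though at risk, which would dilute any procedure-related event proportion. A person who was randomised, never dosed, and then attended would have every procedure and yet fall outside the safety summary. At stake is whether the extension's safety statement describes the people it actually tested.

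**Working it through.** **Inputs.** Parent enrolment 40, deaths by Day 60 7, remaining 33 (all Protocol 6.2); visit at Day 365 ± 90 (5.0); adverse event window 60 days from first product (10.6). The documents do not give the number dosed, the number attending the visit or the number of events. Below I assume that all 40 were dosed, and that 33 (the maximum), 25 or 20 attend.

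**Step 1: the plan's own figure.** 40 − 7 = 33, which agrees with 6.2.

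**Step 2: the denominator on the literal reading.** The set is everyone dosed, so up to 40. The number who can be exposed to a procedure is at most 33. The excess is up to 40 − 33 = 7, or 7/40 = 17.5% of the set, plus any dosed survivor who does not attend.

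**Step 3: effect on a reported proportion.** With n attending, one event is truly 1/n but reads 1/40, so the proportion is multiplied by n/40. With no events, the exact one-sided 95% upper bound is 1 − 0.05^(1/N), with N = 40 on the literal reading and N = n otherwise.

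| Attending n | One event, 1/n | One event, 1/40 | Factor n/40 | Zero-event bound, N = n | Zero-event bound, N = 40 |
|---|---|---|---|---|---|
| 33 | 3.0% | 2.5% | 0.825 | 8.7% | 7.2% |
| 25 (assumed) | 4.0% | 2.5% | 0.625 | 11.3% | 7.2% |
| 20 (assumed) | 5.0% | 2.5% | 0.500 | 13.9% | 7.2% |

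**Step 4: the narrow reading.** If the sentence covers only people who re-consented (8.4), the dead, the decliners and those unable to attend are never in the set. Steps 2 and 3 then do not apply.

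**Step 5: the undosed attendee.** Section 4.1 admits any parent enrolee, dosed or not. The intent-to-treat wording in 6.1 allows for randomised patients who got no drug. Such a person could attend and have all procedures, but fails the dosing rule on both readings.

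**Step 6: the collection window.** The visit falls between Day 365 − 90 = 275 and Day 365 + 90 = 455. If the first dose was close to enrolment (assumed), the window in 10.6 closes at about Day 60, which is 275 − 60 = 215 days before the earliest visit. Section 11.0, by contrast, requires grade 3 or higher events arising on study to be documented whatever their cause. The two sections do not fit together for events at the visit.

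**The case against.** A reader might infer that the seven patients who died are certainly in the denominator. The documents do not support that. Sections 8.1 and 8.4 register and enrol only people who consent to the extension, 4.2 excludes the dead, and 6.2 confines the study to the remaining 33. Read alongside these, the sentence in 6.1 may mean re-consented subjects who had been dosed. Against that, 6.1 does not say so, and 4.2 uses the word subjects for parent enrolees, including those who have died, although it adds the parent protocol number to make this clear. The text is ambiguous.

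A reader might also infer that an event in an undosed attendee would be lost. It would not be, if it is grade 3 or higher: 11.0 has no dosing condition, and the procedure-based stopping criteria in 13.0 apply to any subject. At most the event would be missing from a summary. No document shows that any of the 40 went undosed.

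It is also fair to say that little depends on the denominator. The extension has no safety endpoint and specifies no procedure-event rate. The adverse event proportions in SAP 6.0 belong to the parent trial. The numeric stopping criteria are counts of subjects, and Table 2 reports single events.

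Finally, drug exposure is not irrelevant: Table 2 and 13.0 still mention drug-related or product-related events. That is a reason to keep a dosed set for that purpose, not to use it for procedure safety.

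These points limit the consequences. They do not explain why dosing should define the safety set of a visit at which no drug is given.

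**Conclusion.** The rule in 6.1 selects by the wrong exposure and should be changed. The consequence is modest and partly depends on how the sentence is read.

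- **Literal reading, all 40 dosed:** up to 40 in the denominator against at most 33 who could be exposed. One event reads 2.5% rather than 3.0% at full attendance; the gap widens if fewer attend. Seven is the upper limit for deaths in the set, because the number dosed is not stated.
- **Narrow reading, re-consented subjects only:** this excess disappears.
- **Either reading:** an undosed attendee is left out of the safety summary. This is a gap in the definition, not a known case.

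It would go too far to conclude that the extension's safety results will be materially understated or that events will go unrecorded. The primary endpoint, the planned tests and the stopping criteria are untouched. The more practical problem is that the safety set and the window in 10.6 both look back to the parent trial, so correcting the set alone would still leave it unclear whether visit events are collected.

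**What to change.** Replace the safety sentence in Protocol 6.1 with wording such as: *The safety analysis includes every participant who consented to this extension and began at least one extension procedure, whether or not parent study drug was received, summarised overall and by randomised arm.* Keep the dosed-patient set for parent-trial drug safety, as in SAP 3.1. Here the arm is a descriptive grouping, since the exposure being assessed is the visit.

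At the same time, reconcile 10.6 with 5.0 and 11.0, so that the adverse event period clearly covers the visit at Day 365 ± 90 and events arising there are collected.

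The cost is one sentence in 6.1 and a clarification of 10.6. The new set itself needs no extra data, because consent is already recorded in the database and the visit procedures are the study data. Reported procedure event proportions may look slightly less favourable, because the denominator can only be the people who were exposed.
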